## Appendix D: COVID-19 GUIDANCE

All provisions outlined should be viewed as temporary and will be applicable only for the duration of the pandemic. If any provisions are modified due to the coronavirus (COVID-19) pandemic, please clearly document the planned deviation was due to COVID-19 and document the effective date of the interim measure in the subject's medical records.

In general, the subject and Investigator should together make the best and safest decision for the subject. Due to the requirement for certain individuals to self-isolate, and the issuance of shelter in place policies in a number of metropolitan areas, we recommend all sites contact each subject by telephone or email prior to the scheduled visit to determine if an in-person visit is feasible.

### COVID-19 Screening

Incorporation of the following screening questions to identify potential COVID-19 exposure during the telephone or email contact prior to the scheduled visits are recommended:

- Have you traveled anywhere in the past 14 days?
- Have you had any of the following symptoms in the past 14 days without confirmation as something other than COVID-19 (such as a positive flu test, chronic medical condition, etc.)?
  - Fever greater than 100.4°F (38°C)
  - Cough
  - Difficulty breathing
  - Sore throat
- In the last 14 days, have you lived with, visited, cared for, or been in a room for a prolonged period of time with someone who is under investigation or has been confirmed for COVID-19?

Should a subject respond yes to any of the above questions, it is recommended site personnel identify a resource to direct the subject to. Scheduled visits should be rescheduled if possible; if this is not possible, the visit should be marked as “not done” and reasons should be noted in study files.

### For Subjects who are Unable to Travel to Site

If the subject is unable to travel to the trial site due to COVID-19 infection, self-quarantines, or travel restrictions, we recommend the following procedures be completed by phone, email or telehealth:

- Concomitant medications
- Adverse events
- If available, physical exams may be conducted using telehealth methods

Sites should also determine if home visits can be conducted with visiting nurses or home health aides. If available, safety evaluations (labs, vital signs and ECG [if available]) should be completed. If available, treatment with pembrolizumab may continue; however, treatment with ADU-S100 outside of a clinical setting is not recommended.

### Limited Site Staff

The Sponsor also recognizes that site staff may also be limited during this pandemic. Though we ask that the sites be as compliant with the protocol as possible, we recognize that this might not be feasible at this

time. In this case, priority should be given to the following protocol specific procedures (from the highest to the lowest priority):

1. Administration of pembrolizumab and ADU-S100
2. Concomitant medications, adverse events
3. Safety labs
4. Vital signs, physical examination
5. ECG
6. Tumor imaging

If tumor imaging is not feasible, for example due to shortage of staff, and if the Principal Investigator or designee considers the subjects clinically stable and it's in the subject's best interest, treatment should continue. Images should be taken at the next available opportunity. Reasons for imaging delay should be documented in source documents and the sponsor (or its representatives) should be notified.

If shipping capabilities are no-longer available, sites should hold samples till shipping capabilities are restored. Please refer to the Central Laboratory Manual for appropriate storage conditions **Reduced Visits for Subject Safety**

If it is determined that frequent visits to the site is not safe for the subject, visits whereby treatment (pembrolizumab and/ or ADU-S100) is administered should be prioritized.

### 3 LIST OF ABBREVIATIONS

**Table 1 List of Abbreviations**

Abbreviation	Definition
AE	adverse event
ALT	alanine aminotransferase
AST	aspartate aminotransferase
ATC	Anatomical Therapeutic Chemical
AUC	area under curve
BLQ	below the limit of quantification
BMI	body mass index
CI	confidence interval
CR	complete response
CRS	cytokine release syndrome
CSR	clinical study report
CV	coefficient of variation
DCR	disease control rate
DNA	deoxyribonucleic acid
DODC	duration of disease control
DOR	duration of response
EAS	evaluatable analysis set
EBV	Epstein-Barr virus
EBNA	Epstein-Barr nuclear antigen
ECG	electrocardiogram
ECOG	Eastern Cooperative Oncology Group
eCRF	electronic Case Report Form
EOT	end of treatment
FT3	free tri-iodothyronine
FT4	free thyroxine
HBV	hepatitis B virus
HCV	hepatitis C virus
HIV	human immunodeficiency virus
HNSCC	head and neck squamous cell cancer
HPV	human papillomavirus
iBOR	immune best overall response
ICH	International Council for Harmonisation
iCR	immune complete response
iCPD	immune confirmed progressive disease

---

Abbreviation	Definition
IFN	interferon
Ig	immunoglobulin
IL	interleukin
IP	investigational product
iPR	immune partial response
iRECIST	modified RECIST v1.1 for immune-based therapeutics
iSD	immune stable disease
iUPD	immune unconfirmed progressive disease
IV	intravenous
MedDRA	Medical Dictionary for Regulatory Activities
NCI-CTCAE	National Cancer Institute Common Terminology Criteria for Adverse Events
NE	not evaluable
ORR	objective response rate
OS	overall survival
PFS	progression-free survival
PK	pharmacokinetic
PCR	polymerase chain reaction
PR	partial response
Q1	25 th percentile
Q3	75 th percentile
RECIST	Response Evaluation Criteria in Solid Tumors v1.1
SAE	serious adverse event
SAP	statistical analysis plan
SOD	sum of diameters
SD	stable disease
SI	Système International
SNP	single nucleotide polymorphisms
TEAE	treatment-emergent adverse event
TNF	tumor necrosis factor
TSH	thyroid stimulating hormone
ULN	upper limit of normal
VCA	viral capsid antigen
WHODDE	World Health Organization Drug Dictionary Enhanced

---

## 4 INTRODUCTION

The purpose of this statistical analysis plan (SAP) is to provide comprehensive and detailed descriptions of the methods and presentation of data analyses proposed for Aduro Biotech, Inc. Protocol ADU-CL-20 (A Phase 2 Efficacy and Safety Trial of ADU-S100 and Pembrolizumab in Adults with Head and Neck Cancer). Descriptions of planned analyses are provided in order to avoid post hoc decisions that may affect the interpretation of the statistical analysis. The statistical methods applied in the design and planned analyses of this study are consistent with the International Council for Harmonisation (ICH) guideline *Statistical Principles for Clinical Trials* (E9) (1998).

This SAP will be finalized prior to data analysis and before database lock; a separate document with templates for tables, listings, and figures will include the planned displays for the clinical study report (CSR). Any changes between the statistical methods provided in the clinical study protocol and this SAP will be explained herein; any changes or deviations from this SAP relative to the final analysis will be fully documented in the CSR. Minor changes or deviations from the templates for tables, figures, and listings will not be documented in the CSR.

In this SAP, the Investigational Product (IP) ADU-S100 and Standard of Care pembrolizumab are both considered “study drug.” Throughout the SAP the term “study drug” is interchangeable between ADU-S100 and pembrolizumab. When referring to only one study drug, the SAP will specify ADU-S100 to indicate the IP or specify pembrolizumab to indicate the Standard of Care.

## 5 STUDY OBJECTIVES

### 5.1 Primary Study Objective

The primary objective of this study is to evaluate the clinical efficacy of ADU-S100 administered in combination with pembrolizumab.

### 5.2 Secondary Study Objectives

The secondary objectives of this study are to:

- Characterize safety and tolerability
- Further evaluate clinical activity
- Characterize the pharmacokinetics (PK) of ADU-S100 administered by intratumoral injection following a single dose and multiple doses

### 5.3 Exploratory Study Objectives

The exploratory objectives of this study are to:

- Assess pharmacodynamics, immunomodulatory, and potential prognostic and/or predictive biomarkers
- Perform pharmacogenetic analysis

## 6 INVESTIGATIONAL PLAN

[figure not shown]
### 6.1 Overall Study Design

The ADU-CL-20 study is an open-label, multicenter Phase 2 clinical trial to evaluate the efficacy and safety of intratumoral ADU-S100 (also referred to as MIW815) administered with standard of care treatment (ie, pembrolizumab) in the first-line setting. The multicenter clinical trial will be conducted at approximately 25 sites in North America. Twenty evaluable subjects will initially be enrolled. If the total number responding is greater than or equal to 4, then an additional 14 evaluable subjects will be enrolled in the second stage for a total of 34 evaluable subjects.

The population for this study will consist of adults with metastatic head and neck squamous cell cancer (HNSCC) where pembrolizumab is indicated as the standard of care first line treatment. Individuals with intercurrent illnesses, inadequate organ function, various conditions impacting immune function, or other mitigating factors as detailed in the exclusion criteria will not be enrolled as these factors may interfere with the proposed mode of action of ADU-S100 and pembrolizumab, introduce undue safety risks, or confound interpretation of study results.

The trial design consists of a Screening Period, Treatment Period, and a Follow-up Period as depicted in [Figure 1](#). Screening assessments will be conducted to confirm eligibility and to obtain baseline (pre-treatment) measurements. Screening must be completed within 28 days prior to the first dose of either study drug. An enrollment form will confirm subject eligibility; baseline biopsies will not be performed until enrollment is confirmed. All eligible subjects will receive intravenous (IV) infusions of pembrolizumab (200 mg) and intratumoral injections of ADU-S100 (800 mcg/lesion; up to 2 lesions). During the Treatment Period, study medications will be administered in 21-day dosing cycles until criteria for treatment discontinuation are met, or up to 35 cycles. Tumor responses will be evaluated at 9-week intervals. The Follow-up Period is designed to assess vital status, subsequent anti-cancer therapy, and complete safety reporting requirements.

**Figure 1 ADU-CL-20 Study Design**

Subjects will be requested to complete multiple clinic visits during all dosing cycles. An end of treatment (EOT) visit will occur 30 (+7) days after the last dose of study drug. All EOT visit assessments will be completed prior to commencing any new anti-cancer therapy.

After completion of the EOT visit, follow-up visits will be conducted at 8-week intervals to satisfy protocol-specified safety reporting periods, and collect data on any subsequent cancer-related therapies as well as vital status. Follow-up visits may be conducted at the site or via telephone call, as appropriate.

Subjects who discontinue study drug early for reasons other than progressive disease will complete the EOT visit and will be asked to continue tumor response assessments. Follow-up visits will also be conducted at 8-week intervals for these subjects.

All study visits (and visit windows), assessments, and procedures will be performed as indicated in [Appendix A: Schedule of Events](#). On days when the study drug is administered, assessments will be performed prior to dosing unless otherwise specified.

## 6.2 Determination of Sample Size

The study will include up to 34 evaluable subjects to assess the clinical efficacy of ADU-S100 administered in combination with pembrolizumab in adults with head and neck cancer. Power calculations based on a Simon’s 2-stage minimax design test the null hypothesis that the objective response rate (ORR) is less than or equal to 0.19 versus the

alternative hypothesis that the ORR is greater than or equal to 0.38 with a Type 1 error rate of 0.05 and power of 80%. A sample size of 20 evaluable subjects will be enrolled in the first stage. If the total number responding is greater than or equal to 4, an additional 14 evaluable subjects will be enrolled in the second stage for a total of 34 evaluable subjects. For the second stage, if the total number responding is less than or equal to 10, the effectiveness of treatment based on ORR will be rejected.

If treatment is actually not effective and  $ORR \leq 0.38$ , then the expected sample size is 25.3 evaluable subjects with a 0.456 probability of early termination and a 0.044 probability of incorrectly concluding the treatment is effective (the target for this Type 1 error rate was 0.05 or less). If the treatment is actually effective, there is a 0.200 probability of incorrectly concluding it is not effective (the target for this Type 2 error rate was 0.200 or less).

Subjects who do not complete a response assessment will not be considered evaluable and will be replaced.

The ORR criteria are based on the pembrolizumab first-in-human study in a similar patient population with similar prior treatment where the response rate was approximately 19% (Burtneß et al. 2018; Rischin et al. 2019).

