### 12.1 Sample Size Determination

The original sample size was based on a Simon's 2-stage minimax design (Simon 1989) test the null hypothesis that the objective response rate (ORR; complete response [CR] and partial response [PR]) per Response Evaluation Criteria in Solid Tumors (RECIST) v1.1) is less than or equal to 0.19 versus the alternative hypothesis that ORR is greater than or equal to 0.38, with a Type 1 error rate of 0.05 and power of 80%.

Because of truncated enrollment, the total sample size will be limited to approximately 20 evaluable subjects as planned for the first stage.

Subjects who do not complete a response assessment will not be considered evaluable.

The ORR criteria are based on the pembrolizumab first in human study in a similar patient population with similar prior treatment where the response rate was approximately 19% (Burtneß et al. 2018; Rischin et al. 2019).

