#### 7.4.4 *Primary Efficacy Endpoint Analysis Methods*

The primary efficacy endpoint is ORR as defined in [Section 6.4.1.1](#) and will be summarized for the All Treated Population.

Summaries of ORR will include the number and percentage of subjects with an objective response and the corresponding two-sided 95% confidence interval (CI) based on the exact binomial method (Clopper-Pearson). Waterfall plots will be provided showing the best overall tumor response. A swimmer plot of disease status for RECIST and iRECIST will be provided. Also, a spider plot of percent change in tumor size relative to baseline will be provided.

Tumor diameters recorded on the Target and New Lesions CRF pages will be utilized for analysis summaries. Diameters recorded on the Dose Administration CRF page or the Injected Lesion Photo CRF page will not be utilized for analysis.

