#### 7.4.6.4 *Interim Analyses and Data Monitoring*

There are no interim analyses planned, nor is there a plan to establish a data monitoring committee for this study.

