#### 7.4.6.6 *Multiple Comparisons/Multiplicity*

There will be no adjustments for multiple comparisons in the efficacy analysis for this study. Results are descriptive in nature and there will be no formal comparisons made.

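### SAP 6.1 and 6.2 still describe a 34-subject two-stage test with 80% power for a trial capped at about 20 with no planned test; 6.2 also misstates the expected sample size and the null response rate

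*SAP*

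**What the plan says.** SAP 6.1 says 20 evaluable subjects will be enrolled and that, with four or more responders, "then an additional 14 evaluable subjects will be enrolled in the second stage for a total of 34 evaluable subjects". SAP 6.2 repeats this, gives a null ORR of at most 0.19 against an alternative of at least 0.38, a type I error of 0.05 and power of 80%, and adds the final rule: "if the total number responding is less than or equal to 10, the effectiveness of treatment based on ORR will be rejected". It then describes the case in which treatment is not effective, labels it ORR of 0.38 or less, and says that "then the expected sample size is 25.3 evaluable subjects with a 0.456 probability of early termination", with a 0.044 chance of wrongly declaring the treatment effective. The type II error is given as 0.200.

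The protocol differs. Its synopsis gives up to 20 subjects. Section 12.1 refers to the Simon design as the original basis and continues: "Because of truncated enrollment, the total sample size will be limited to approximately 20 evaluable subjects as planned for the first stage".

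The SAP's analysis sections contain no test. Section 7.4.4 reports the number and percentage of responders with an exact two-sided 95% Clopper-Pearson interval. Section 7.4.6.1 calls all results descriptive. Section 7.4.6.4 says "There are no interim analyses planned", and 7.4.6.6 says "Results are descriptive in nature and there will be no formal comparisons made".

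SAP 4 undertakes that "Any changes between the statistical methods provided in the clinical study protocol and this SAP will be explained herein". Section 7.6, which lists the changes, covers the analysis sets and duration of disease control but not sample size.

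**The concern.** There are two separate problems.

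The first is that the design text does not fit the trial. With enrolment capped at about 20 there is no second stage, so the cut at 10 of 34 can never be applied and the 80% power is not available. The same SAP plans neither a test nor an interim look.

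The second is that one sentence in 6.2 is wrong whichever protocol version applies. Its expected sample size conflicts with the early-termination probability beside it, and its condition names the alternative response rate as the not-effective case.

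The stake is interpretation. A reader could carry 80% power into a report on about 20 subjects, quote null properties as if they held at ORR 0.38, or treat four responders in 20 as a success when it was only a rule for continuing.

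**Working it through.** **Inputs.** From SAP 6.2: first stage n1 = 20, stop at 3 or fewer responders; total n = 34, not effective at 10 or fewer; p0 = 0.19, p1 = 0.38. Binomial probabilities are exact.

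**Formulas.**
- Probability of early termination: PET(p) = P(X1 ≤ 3 | 20, p).
- Expected size: E[N] = 20 + 14 × (1 − PET).
- Probability of declaring the treatment effective: the sum over x = 4 to 20 of P(X1 = x) × P(X2 ≥ 11 − x | 14, p).

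**Reproducing the plan's own figures.** At p = 0.19, the probabilities of 0, 1, 2 and 3 responders in 20 are 0.0148 + 0.0693 + 0.1545 + 0.2175 = 0.4561.

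| Quantity | Printed in SAP 6.2 | At ORR 0.19 | At ORR 0.38 |
|---|---|---|---|
| PET | 0.456 | 0.4561 | 0.0245 |
| P(declare effective) | 0.044 | 0.0446 | 0.8001 |
| Expected N | 25.3 | 27.61 | 33.66 |

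The type II error at 0.38 is 1 − 0.8001 = 0.200, as printed. The 0.044 is a truncation of 0.0446, which would round to 0.045; this is trivial. A search over two-stage designs confirms that 3/20 then 10/34 is the minimax design for these inputs. The boundaries, PET and power are therefore right, and only two items fail.

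**Expected N.** From the printed PET alone, 20 + 14 × 0.544 = 27.6. To obtain 25.3 with 20 and 34 subjects, PET would have to be 1 − 5.3/14 = 0.621. Moving the first-stage cut does not recover it: stopping at 4 or fewer gives 24.6, and at 2 or fewer gives 30.7. With the final rule held at 10/34, a first stage of 18 subjects stopping at 3 or fewer does give 25.3, but its PET is 0.545 and its power 0.793, so it is not the stated design.

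**Null label.** The printed PET and type I error match the 0.19 column. At 0.38, the value printed as the not-effective case, the design declares the treatment effective with probability 0.80.

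**What about 20 subjects can support (illustration only; no document plans this test).** Take the smallest cut k with P(X ≥ k | 0.19) ≤ 0.05, then its power at 0.38. The range of n is an assumption: 16 patients had been treated by 17 December 2020 (Protocol 5.2.2), and 22 allows a slight overrun of the cap.

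| n | Cut k | Type I error | Power at 0.38 |
|---|---|---|---|
| 16 | 7 | 0.020 | 0.41 |
| 18 | 7 | 0.040 | 0.56 |
| 20 | 8 | 0.024 | 0.51 |
| 22 | 8 | 0.043 | 0.64 |

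Power does not rise steadily with n because the cut moves in whole responders.

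Read as a success rule, four or more of 20 would be met with probability 1 − 0.456 = 0.544 when the true ORR is 0.19.

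Exact 95% intervals at n = 20:
- 3/20: 0.032 to 0.379
- 4/20: 0.057 to 0.437
- 7/20: 0.154 to 0.592
- 8/20: 0.191 to 0.639

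Any result from 4 to 7 responders gives an interval containing both 0.19 and 0.38.

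**The case against.** The strongest reply is version lag. The SAP's schedule of events still has lesion photography, PK and tissue sampling, 8-weekly follow-up and the imaging change at 45 weeks. The current protocol has removed the photography and sampling by Amendment 4, has no 8-weekly follow-up column, and changes imaging at 27 weeks. SAP 6.5.3 refers to Amendments 1, 2 and 3 or beyond and never names Amendment 4. The SAP's date is not visible. If it was written before the cut, 6.1 and 6.2 described the protocol then in force, and 7.6 had no sample-size difference to list. This is plausible, and it means that the omission from 7.6 does not prove an oversight at drafting. It does not remove the need to bring the SAP into line with the protocol.

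Three further points carry weight. The protocol itself is clear about truncation, and SAP 6.2 ties the 80% to the 34-subject design, so a careful reader of both documents would not be misled about size. A Simon first-stage count is not always called an interim analysis, so the conflict with 7.4.6.4 is softer than the lack of any analysis in 7.4.4 matching the 10-of-34 rule. And the primary denominator in SAP 7.4.4 is the All Treated Population, so intervals at exactly 20 are indicative only.

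None of this touches the two errors in 6.2. They arise within that section's own figures.

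**Conclusion.** The concern holds. The expected sample size under the null is 27.6, not 25.3, an understatement of 2.3 subjects, and the not-effective case should be ORR of 0.19 or less. Both conclusions need only the figures printed in SAP 6.2 and the binomial distribution.

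The 34-subject size, the 80% power and the 10-of-34 rule do not describe a trial limited to about 20 evaluable subjects and analysed descriptively. The illustrative power of 0.51 at n = 20 (0.41 to 0.64 across the sizes tabulated) assumes a one-sided exact test at 5% that nobody plans; it shows only how far the stated 0.80 is from what this size can deliver.

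The consequence is confined to how the design is described and how results may be read. It should be corrected, but it does not threaten the analysis.

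**What to change.** Make these changes in the SAP:

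- **6.1 and 6.2, status and size:** label the two-stage design as the original one, now superseded, and give the size as about 20 evaluable subjects in line with Protocol 12.1.
- **6.2, figures for the original design:** change the not-effective condition from 0.38 to 0.19 and the expected sample size from 25.3 to 27.6.
- **6.2, interpretation:** state that no test with 80% power remains and that the primary result is the ORR with its exact 95% interval, as 7.4.4 already provides. Say that four of 20 was only a continuation rule and does not show an ORR above 0.19. Any power or interval width should be given as illustrative for the number actually analysed, not as a new decision threshold.
- **7.6:** record the change in sample size and the loss of the second stage.

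The cost is wording only. No data collection, estimate, interval or table changes.
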